##### **2.2.5.2 PRE-TREATMENT EVALUATIONS AND DATA COLLECTION**

Pre-treatment evaluations and data collection will include:

- Radiographic studies for verification of DDD;
- AP and lateral X-rays (plain films);
- Flexion-extension X-rays (used to determine range of motion);
- Lateral bending films;
- MRI or CT (investigational group only)
- Radiographic core lab evaluations;
- Dysphagia Handicap Index (investigational group only);
- Study related medical history and physical examination;
- DXA (if indicated as described in Section 2.2.3.2);
- NDI assessment;
- SF-12v2 Health Survey (investigational group only);
- VAS pain assessments (neck and arm; neck, left arm and right arm (investigational group only));
- Neurologic evaluation;
- Study related medication history and
- Work status.

Radiographic studies used for verification of DDD, DEXA scans and baseline MRI or CT may be taken up to 6 months prior to the pre-treatment evaluation. Flexion/extension X-rays and AP & lateral X-rays and lateral bending X-rays must be taken no sooner than 90 days prior to the pre-treatment evaluation. *All other pre-treatment measurements* must be done no sooner than 30 days prior to the pre-treatment evaluation.

The neurologic evaluation will include a motor and sensory assessment, reflex responses and the determination of the presence or absence of dysphagia, dysphonia, clumsiness, foot drop, atrophy, cramping, muscle spasms, numbness and gait abnormality.

For the purposes of this clinical study, only medications taken or administered for the following will be recorded on the Case Report Form:

---

- Pain (any type);
- Inflammation (any type);
- Muscle relaxation;
- Numbness &/or tingling;
- Hormonal replacement therapy and
- Other medications related to or given for the subject's spinal condition.

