It is assumed for the purpose of sample size analysis that at least 80% of the 116 evaluable ACDF controls, that is, N=93 will be remaining after the iterative PS sub classes determination and that the success rate will be 74.1% in the retained sample. It is possible that the effective sample size will be slightly higher since, as described below, multiple imputation will be used to address missing data from the prior study.

In order to have a sufficient size sample for safety profile evaluation, 150 investigational device patients will be enrolled. For the purpose of sample size evaluation, this value is reduced by 15% to account for loss-to-follow-up. It is further assumed that no more than 10% of the analysis set will be excluded based on design of the PS sub classes, reducing the evaluable sample size from 128 to 115.

The assumptions above imply an expected device group difference equal to equal to 7.3% for the primary endpoint. The study is designed to demonstrate non-inferiority using a non-inferiority margin equal to -10.0%.

If there were N=115 Simplify® Disc patients, then a “two-group large-sample normal approximation test of proportions with a one-sided 0.05 significance level will have 91% power to reject the null hypothesis that the test and the standard are not equivalent (the difference in proportions,  $\pi_1 - \pi_2$ , is -

0.10 or farther from zero in the same direction) in favor of the alternative hypothesis that the proportions in the two groups are equivalent, assuming that the expected difference in proportions is 0.073 and the proportion in the standard group is 0.741 [REDACTED]).

Thus, as long as the superiority margin between the Simplify® Disc and ADCF about the same as observed between Kineflex|C and ADCF, then N=115 patients included in the Simplify® Disc analysis set will result in adequate (i.e.,  $\geq 80\%$ ) statistical power. As noted above, this sample size is conservatively increased by 15% to account for potential loss-to-follow-up and by 10% to account from exclusions during the PS modeling. Therefore, the target prospective enrollment is N=150.

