#### 2.2.6.5 PROPENSITY SCORE MODELING APPROACH

A sequential heuristic for PS modeling will be used to determine the PS model (Maislin and Rubin 2011). The heuristic is capable of producing balance between groups that are prerequisite for valid efficacy comparisons. The heuristic includes a trio of "stages" that may be repeated as many times as necessary. These stages include (1) estimating a main effects PS model; (2) identification of required higher order terms through evaluation of within subclass bias effect sizes and other relevant PS diagnostic information; and (3) exclusion of subjects in one treatment group with insufficient 'covariate overlap'. The magnitudes of standardized effect sizes for group differences in linear, squares, and cross-product terms within subclasses provide key insight into what additional terms the PS model must have in order to achieve adequate within-subclass balance between treatment groups. Specific choices made during the model building process pose no concern for Type I error inflation because these analyses do not involve any outcome data. In this way the sequential model-building exercise should be viewed as part of the 'design of the observational study'. The result of the PS modeling process is an assignment of patients from both groups to sub classes defined on the basis of the estimated propensity scores. When certain diagnostic properties hold, the covariate distributions are identical between the investigational and control groups within each of the PS quintiles. Therefore, within PS quintile, patients are essentially equally likely to be in either group based on relevant covariates and analyses can proceed as if patients were randomized. This is accounted for by including a  $df=4$  factor for propensity score quintile in analysis of variance and regression models. The ability of the propensity score model to balance observed covariates will be graphically assessed.

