2.2.6.11 SECONDARY ENDPOINTS

Secondary endpoints include:

- Clinically significant improvement in one or more radicular symptoms or myelopathy at 24 months compared to baseline for the investigational Simplify® Disc and 24 months compared to baseline for the control ACDF. The data collected will reflect the number of patients who improved (numbers will be stratified to reflect clinical improvement), who remain unchanged, and who deteriorated at each study time point. These endpoints will be graded and defined as follows:
  - A visual analog scale (VAS) will be used to evaluate each of the following pain locations:
    - Neck and arm pain (to allow comparison to ACDF control)
    - Neck pain
    - Left arm pain;
    - Right arm pain;

Changes of at least 20 mm on a 100 mm scale will be regarded as clinically significant.

- Motor status - A change of one or more grade levels in muscle strength will be regarded as clinically significant.

- Sensory status - Sensation will be graded as normal or abnormal (diminished or absent). Any changes from abnormal to normal or absent to diminished will be regarded as clinically significant improvement..
- Time to recovery (time to first 15-point NDI improvement).
- Disc height at 24 months compared to baseline for the investigational Simplify® Disc and at 24 months compared to baseline for the control ACDF, as measured by standard lateral radiograph (spot film, distance of 6 feet, centered at C5 with patient upright).
- Adjacent level deterioration at 24 months compared to baseline for the investigational Simplify® Disc and at 24 months compared to baseline for the control ACDF.
- Displacement or migration of the device; only changes of > 3 mm will be considered significant due to the margin of error in radiographic determination of displacement distances.
- Treatment satisfaction at 24 months for the investigational Simplify® Disc and at 24 months for the control ACDF.
- Health Survey (SF-12v2) for the investigational Simplify® Disc at 24 months compared to baseline.
- Dysphagia Handicap Index (DHI scale) for the investigational Simplify® Disc at 24 months compared to baseline.
- Facet deterioration for the investigational Simplify® Disc at 24 months compared to baseline..

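### In the visible text, the between-arm pain comparison (combined neck-and-arm VAS) is summarised by 20 mm change counts; adding a baseline-adjusted mean difference would use the same data more precisely.

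*Combined protocol and SAP*

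**What the plan says.** Section 2.2.6.11 opens its secondary endpoints with clinically significant improvement in radicular symptoms or myelopathy at Month 24, and describes the output as counts: "The data collected will reflect the number of patients who improved (numbers will be stratified to reflect clinical improvement), who remain unchanged, and who deteriorated". This is to be shown at every study time point. For VAS the grading rule is "Changes of at least 20 mm on a 100 mm scale will be regarded as clinically significant". Motor and sensory status have their own grading rules beside it.

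The change is measured from baseline in both groups; for the control the wording is "24 months compared to baseline for the control ACDF". One pain score is identified as shared between the arms: "Neck and arm pain (to allow comparison to ACDF control". The separate sites are collected in the Simplify arm alone; section 2.2.5.2 lists "VAS pain assessments (neck and arm; neck, left arm and right arm (investigational group only".

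The schedule in section 2.2.5.5 has VAS before surgery and at every visit after it. Section 2.2.6.5 provides in general terms for "including a $df=4$ factor for propensity score quintile in analysis of variance and regression models", without naming VAS or any baseline covariate. No visible text gives a VAS mean, mean difference, confidence interval, test, SD, assumed effect or power. Sections 2.2.6.9 and 2.2.6.10 are redacted in full.

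**The concern.** VAS pain is measured in millimetres on a 100 mm scale, before and after surgery. A count at a 20 mm change uses only part of that information, because it records which side of a cut a patient falls on. Nor does it adjust for how severe the pain was at the start, although baseline VAS usually explains some of the variation in the Month 24 score. The control group is historical, so baseline VAS in the model would also deal with any imbalance in that score left within PS quintiles. Section 2.2.6.3 says that the propensity score is meant to remove bias and not to add precision, so the quintile factor is not intended to recover what the cut loses.

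At stake is how precisely the trial can describe the pain difference between Simplify and ACDF. The primary endpoint sets the sample size, so the choice of analysis is the practical way to sharpen this comparison. The visible text cites no source for the 20 mm threshold, whereas section 2.2.6.3 does cite one for the 15-point NDI threshold. The point does not depend on 20 mm being wrong, and the threshold is not disputed here.

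**Working it through.** **Inputs from the plan (2.2.6.4).** Analysable patients: 115 Simplify and 93 ACDF. Power statement: "with a one-sided 0.05 significance level will have 91% power to reject the null hypothesis", where "the expected difference in proportions is 0.073 and the proportion in the standard group is 0.741". The Simplify rate is therefore 0.741 + 0.073 = 0.814, and the margin is 0.10.

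**Step 1: reproduce the plan's own figure.** This is the primary endpoint; it confirms the sample sizes and the one-sided level.

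- SE = √(0.814×0.186/115 + 0.741×0.259/93) = 0.0581
- Power = Φ((0.073 + 0.10)/0.0581 − 1.645) = Φ(1.33) = 90.8%, or 91.1% with a pooled null SE. The stated 91% reproduces.

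**Step 2: assumed VAS inputs.** The documents give none. Assume baseline SD 20 mm, follow-up SD 28 mm, correlation 0.3, true difference 10 mm and one-sided 0.05, with normal scores.

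- SD of change = √(20² + 28² − 2×0.3×20×28) = √848 = 29.12 mm
- Residual SD after baseline adjustment = 28×√(1 − 0.3²) = 26.71 mm
- √(1/115 + 1/93) = 0.1395

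**Step 3: power of each analysis.**

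| Analysis | Calculation | Power |
|---|---|---|
| ANCOVA | SE = 26.71×0.1395 = 3.725 mm; 10/3.725 = 2.685; Φ(2.685 − 1.645) | 85% |
| Mean change, no covariate | SE = 29.12×0.1395 = 4.061 mm; 10/4.061 = 2.462; Φ(2.462 − 1.645) | 79% |
| 20 mm responders, control mean improvement 20 mm | rates Φ(0) = 0.500 and Φ(10/29.12) = 0.634; SE 0.0686; 0.134/0.0686 ≈ 1.959; Φ(1.959 − 1.645) | 62% |
| 20 mm responders, control mean improvement 40 mm | rates Φ(20/29.12) = 0.754 and Φ(30/29.12) = 0.849; SE 0.0558; 0.0946/0.0558 ≈ 1.696; Φ(1.696 − 1.645) | 52% |

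A pooled null SE gives 62% and 53% for the last two rows. The loss against ANCOVA is about 23 and 33 points. As precision, (1.959/2.685)² = 0.53 and (1.696/2.685)² = 0.40: the responder comparison carries roughly the information of an ANCOVA on 53% or 40% of the patients.

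**Step 4: a second route.** Use the plan's composite success rates as stand-in responder rates, for illustration only.

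- Responder comparison: Φ(0.073/0.0581 − 1.645) = 35%
- Implied standardised difference: Φ⁻¹(0.814) − Φ⁻¹(0.741) = 0.893 − 0.646 ≈ 0.246
- Full scale, SE = √(1 − r²)×0.1395: 55% at r = 0, 58% at r = 0.3, 65% at r = 0.5

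**Step 5: how far the size moves.** One-sided loss of the 20 mm responder comparison against ANCOVA, with control mean improvement 20 to 50 mm and true difference 5 to 15 mm:

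- Equal baseline and follow-up SDs, SD of change 25 to 35 mm, correlation 0.2 to 0.5: loss 4 to 54 points, median 29. Dichotomising alone, against unadjusted mean change, accounts for a median of 17 points; the rest is covariate adjustment.
- Baseline SD 15 to 25 mm, follow-up SD 25 to 28 mm, correlation 0.1 to 0.5: loss 1 to 49 points, median 24. Of these scenarios, 48% lie between 15 and 30 points, 18% below and 34% above.
- Simulation with scores held within 0 to 100: loss 14 to 39 points. Scoring improved, unchanged and deteriorated as three ordered categories recovered at most about 3 points.

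These figures ignore the variance from PS stratification and from missing data, which would affect both analyses.

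**The case against.** The strongest reply has four parts.

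- **The plan may already do this.** Two sections immediately before the secondary endpoints are redacted, and the reference to analysis of variance in 2.2.6.5 suggests continuous outcomes. A reader might infer that VAS is reported only as counts; the documents cannot show that. This stands, and it limits the point to the visible text.
- **The counts hold more than a single cut.** A reader might infer that the baseline value is thrown away, or that a 21 mm and a 70 mm fall must count the same. Neither is supported: change is taken from baseline, and improved patients are to be stratified. The strata are not described, however, and no visible model includes baseline VAS as a covariate.
- **The endpoint is a responder question.** Clinically significant improvement needs a threshold, and a mean difference answers something else. This is a good reason to keep the counts. It is not a reason to omit the mean difference for a score collected so that the arms can be compared.
- **No VAS test or power is stated.** A reader might infer that the trial is set up to miss a real pain difference. That presumes a test which the visible plan does not specify. Power here is a measure of precision, and the success criterion (2.2.6.2) and superiority test (2.2.6.6) do not involve VAS.

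**Conclusion.** The point holds as a low-cost improvement. In the visible text, the pain score shared by the two arms is summarised by counts around a 20 mm change, with no full-scale estimate and no adjustment for baseline VAS. A baseline-adjusted analysis was more precise in every scenario tried.

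The size is conditional. In the worked case (115 versus 93, one-sided 0.05, SDs 20 and 28 mm, correlation 0.3, difference 10 mm) it is about 62% or 52% power against 85%. Across wider assumptions the loss is about 1 to 54 points, with medians of 24 and 29. A reader might take a narrow band such as 15 to 30 points as the answer, but the documents contain no VAS figures from which to fix one, and about half of the scenarios in one grid fall outside it. The effect is confined to the precision of a secondary comparison.

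**What to change.** In 2.2.6.11, add as the between-arm VAS analysis a linear model of the Month 24 combined neck-and-arm VAS with device group, baseline VAS and the PS-quintile factor (df = 4). Report the adjusted mean difference with its confidence interval. Keep the 20 mm improved, unchanged and deteriorated counts as the responder display.

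The cost is a few lines of text and one extra model of a kind that 2.2.6.5 already foresees, with no new patients, visits or data. The drawback is that a difference in millimetres is less directly interpretable than a responder rate, which is why the counts stay. If a redacted section already specifies this analysis, a cross-reference from 2.2.6.11 is enough.

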#### 2.2.6.12 OTHER OUTCOMES

Other outcomes to be measured include:

- Duration of hospitalization;
- Blood loss;
- Operative time;
- Range of motion in flexion/extension at the operative level. Cobb angle measurements of the functional spinal unit will be made. Differences in range of motion of at least 2 degrees when compared to baseline will be considered clinically significant. Assessments will include comparison of range of motion at 24 months to baseline for the Simplify® Disc and at 24 months compared to baseline for the control ACDF and to normal range of motion at the operative level, based on White and Panjabi. Evaluation of these criteria will be based on anterior/posterior, lateral, and flexion/extension X-rays.
- In vivo endplate thickness analysis on 25 subjects.

Radiographs will be used to monitor the occurrence of some of the above adverse events, including subsidence of the device into the adjacent disc or other changes in the implant, and spinal instability. In addition, at each visit, after the subject has had an opportunity to spontaneously mention any problems, the investigator will elicit information concerning adverse events by asking standard questions. Adverse events considered unusual for the patient population (i.e., occurring with greater frequency than anticipated or with greater severity than anticipated), key to safety or efficacy, or device related will require detailed reporting on the appropriate case report form.

#### 2.2.7 SAFETY ASSESSMENT

##### 2.2.7.1 ADVERSE EVENTS

An adverse event is defined as any clinically significant undesirable clinical occurrence in a subject. Adverse events, whether or not device related, must be reported on the appropriate case report form. Adverse events will be classified based on seriousness, relationship to device and procedure, and severity by the study investigator. Any adverse event that occurred prior to treatment with the medical

---

32 White and Panjabi: Clinical Biomechanics of the Spine. 2nd ed. Philadelphia, JB Lippincott Co.,1990.

device will be documented in the patient's pre-operative medical history. Only adverse events which are new or have worsened during the course of this study will be evaluated in the safety assessment.

### **2.2.7.2 SERIOUS ADVERSE EVENTS (SAE)**

#### **2.2.7.2.1 Description**

A Serious Adverse Event is an adverse event which:

1. Led to a death,
2. Resulted in life threatening illness or injury,

NOTE: the term "life-threatening" refers to an event in which the patient was at a risk of death at the time of the event; it does not refer to an event which hypothetically might have caused death if it were more severe.

3. Resulted in subject hospitalization or prolongation of existing hospitalization,
4. Resulted in subject disability or permanent damage or required intervention to prevent permanent impairment/damage.

### **2.2.7.3 UNANTICIPATED ADVERSE DEVICE EFFECTS (UADE)**

#### **2.2.7.3.1 Description**

An Unanticipated Adverse Device Effect is any serious adverse effect on health or safety or any life threatening problem or death caused by, or associated with, a device, if that effect, problem, or death is not identified in nature, severity, or degree of incidence in this Protocol; or any other unanticipated serious problem associated with a device that relates to the rights, safety, or welfare of the subjects.

#### **2.2.7.3.2 Reporting**

Serious Adverse Events and Unanticipated Adverse Device Effects must be reported to the Sponsor, as soon as possible, but in no event later than 10 working days after the Investigator first learns of the effect. SAEs and UADEs must also be reported to the approving IRB per the IRB's reporting requirements.

### **2.2.7.4 POTENTIAL RELATIONSHIP OF ADVERSE EVENTS**

Investigators will be asked to assess the potential relationship of the adverse event to the implanted device and to the procedure and classify the causality of the event according to the following definitions.

- **Definitely Related:** An adverse event that has a strong causal relationship. An adverse event that follows a strong temporal relationship to the use of the device or the procedure, follows a known response pattern, and cannot reasonably be explained by known characteristics of the subject's clinical state or other therapies.
- **Probably Related:** An adverse event that potentially has a causal relationship. The adverse event has a reasonable temporal relationship to the use of the device or the procedure and alternative etiology is less likely compared to the potential relationship to the use of the device or the procedure.
- **Possibly Related:** An adverse event that potentially has a causal relationship. The adverse event has a reasonable temporal relationship to the use of the device or the procedure but alternative etiology is equally likely compared to the potential relationship to the use of the device or the procedure.
- **Not Related:** An adverse event without any apparent causal relationship. The adverse event is due to the underlying disease state or is due to concomitant medication or therapy not related to the use of the device or the procedure.
- **Unknown Relationship:** If the adverse event cannot be determined to have a causal relationship, it will be classified as unknown.

#### 2.2.7.5 ASSESSMENT OF SEVERITY

- **Mild:** event/symptom is transient and well tolerated by the patient.
- **Moderate:** event/symptom causes discomfort and interferes with routine activities of the patient.
- **Severe:** event/symptom interferes considerably with the routine activities of the patient or causes inability to work.
- **Life-Threatening:** refers to an event in which the patient was at a risk of death at the time of the event; it does not refer to an event which hypothetically might have caused death if it were more severe.

#### 2.2.7.6 CLINICAL EVENTS COMMITTEE

The Clinical Events Committee (CEC) will adjudicate all adverse events. This will include all UADEs, SAEs secondary surgeries at the index and adjacent levels, adverse events determined to be

“severe”, and adverse events deemed definitely, probably and possibly related or with an unknown relationship to the device or procedure. The CEC will review investigator assigned neurological status at 24 months to determine whether it meets the criteria for primary endpoint failure as defined as new or worsened decline in neurological status compared to baseline which persists to 24 months based on assessments of motor, sensory, reflex, clumsiness, atrophy, cramping, spasms, numbness, dysphagia, dysphoia, and myelopathic gait abnormality.

The CEC may determine neurologic status has declined based on changes including:

- Motor Assessment: shift of -1.
- Sensory Examination: shift from normal to abnormal; abnormal to increased abnormality.
- Reflex Response: shift from Normal to anything else; hyporeflexive to absent; hyporeflexive to hyperreflexive or hyperreflexive to hyporeflexive.
- Clumsiness, Atrophy, Cramping, Spasms and Numbness: shift from absent to present.
- Dysphagia (difficulty swallowing) and Dysphonia (difficulty with producing sounds resulting in hoarseness, weakness, harshness, roughness and/or breathy sound): any worsening.
- Myelopathic GaitAbnormality Class: any worsening
- Assessment: Does the CEC agree with the investigator assessment

Adverse events determined to be definitely related to the device system or device component will be further evaluated for potential classification as a ‘Major Adverse Event’ as defined in section 2.2.6.1 of this protocol.. The CEC will also adjudicate all protocol deviations. The CEC will consist of three spine surgeons who are not affiliated with the Sponsor or who are not participating in the study. The CEC protocol is designed to mirror the CEC protocol used for the control fusion patients. The recommendations of the CEC override the investigator’s classification and become part of the clinical trial data set.

